interventions.(35, 42) In addition, adding a functional warm-up program, has shown to reduce injuries by 40%.(43-46). RS also builds social capital and is associated with positive motivational factors.(47) The physiologic and behavioral aspects of RS associated with health improvements are summarized by the Football (soccer) is Medicine collaborative we belong to.(24)

Protocol Synopsis

Study Design: A randomized controlled trial to compare two lifestyle intervention deliveries and their effect on bone health and diet and physical activity related measures.

Planned Sample Size: 20 subjects

Subject population: Inclusion criteria: 1) Men aged 18-79 years; 2) PCa survivors that had at least 6 months of hormone therapy (i.e. ADT with testosterone lowering agents) within the past 10 years; 3) not engaged in soccer practice or other exercise or lifestyle intervention program for the past 12-months; 4) Availability of smartphone to receive text messages; 5) Treating Oncologist clearance 6) ability to read in English or Spanish and provide informed consent; **Exclusion criteria:** 1) BMI > 40 kg/m²; 2) resting BP ≥170/100 at screening or uncontrolled hypertension; 3) any mobility issues or exercise program contraindications (48); 4) a recent (i.e., within 12 months) myocardial infarction, diagnosis of congestive heart disease, other active cancer 5) bone or organ metastases, 6) chemotherapy within past 6 months; 7) Therapies and diseases of bone unrelated to PCa e.g. systemic glucocorticoids, bisphosphonates, teriparatide, denosumab, osteomalacia; osteosarcoma; Paget's disease; systemic lupus erythematosus; inflammatory bowel diseases, rheumatoid arthritis; thyroid/parathyroid disorder or mental illness.8) Not COVID-19 vaccinated

Specific Aims

Aim 1: We will conduct a single-arm clinical trial over 3 months, among PCa survivors that had at least 6 months of hormone therapy (i.e. ADT with testosterone lowering agents) within the past 10 years. Participants (n=20) will be offered an intensive intervention including RS programming and lifestyle education. The group will receive RS, consisting of small-sided (5vs5) conditioning drills and games, adapted to the population (60-minute sessions twice/week). We will evaluate pre vs post differences over 3-months in:

(Aim 1a): Primary outcome: lumbar spine BMD at 3-months.

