(Aim 1b): Secondary outcomes: impact on additional markers of bone health including total hip BMD and bone turnover markers (Osteocalcin (a marker of bone formation) and C-terminal telopeptide of collagen (CTX) a bone resorption marker), body composition (weight, BMI, % body fat, waist circumference, lean body mass), cardiometabolic markers (resting heart rate and blood pressure), functional markers (aerobic capacity, muscle strength), behavioral factors (diet and PA self-efficacy, dietary intake, smoking and alcohol habits, weekly steps, sedentary and sleep time) and patient-reported quality of life and depression symptoms.

Aim 2: To assess implementation feasibility and evaluate overall efficacy to increase engagement and adherence with PA, we will evaluate between-group differences over 3 months in:

(Aim 2a): compliance with recommendations of 150 minutes of moderate-to-vigorous PA/week.

(Aim 2b): To assess the RS program adherence and tolerance, we will monitor session attendance, attrition rates, injuries or adverse events, use surveys for assessing participant program satisfaction and behavior change self-efficacy

Research Design:

Organizational structure of study team: This study was investigator initiated and proposed to the Winship Cancer Institute prostate cancer funding opportunity at Emory University as part of an internal pilot grant. The funder's expectation was for the investigator to conduct feasibility or pilot research to support a larger grant. Funder will provide a speedtype for all expenses related to the study.

Setting: All assessments will be conducted at the Emory University Hospital Georgia CTSA GCRC location (baseline and post intervention). Those randomized to the soccer intervention will attend soccer sessions at a local soccer field (either Dunwoody Elementary or the Atlanta Silverbacks indoor facility), no permission is

needed to conduct the study, but field owners are aware of the study be conducted. All data will be collected on paper and transferred to a REDCap database at Emory University Rollins School of Public Health.

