Study Assessments. Prior to testing, subjects will be asked to refrain from physical activity for 48 hours prior to test day, refrain from alcohol 24 hour prior to testing, and refrain from caffeinated drinks, smoking and other stimulants one hour prior to testing. Assessments will be conducted at baseline and post intervention at the Emory University Hospital Georgia CTSA research center (GCRC). Blood pressure, both systolic and diastolic blood pressure will be measured while sitting using a calibrated electronic blood pressure sphygmomanometer prior to any activity and after five minutes of rest., height and weight, waist circumference, aerobic and musculoskeletal fitness assessments will be performed. Bone mineral density will be measured by dual x-ray absorptiometry (DXA) scan at the lumbar spine (L2-L4) and total hip. Body composition will also be determined by DXA scan in the Bionutrition Unit of the GCRC. Venipuncture will be performed by the research nurse for bone turnover markers (Osteocalcin (a marker of bone formation) and C-terminal telopeptide of collagen (CTX) a bone resorption marker), a total testosterone level if not included in a recent clinic visit, and to bank one tube of plasma for future metabolomics studies. In addition, questionnaires will be used for self-reported physical and mental health, quality of life, PA and diet self-efficacy, program satisfaction and injuries. Dietary recalls will be conducted at baseline and 26 weeks by trained staff and analyzed using Nutrition Database System for Research.(49) In addition, both groups will also be asked to wear a Garmin fitness tracker for the duration of the study to measure steps and moderate and vigorous activity. Once baseline measurements are complete and 20 participants have completed they will be randomized to either the soccer group or the mobile health (mHealth) group. Participants in the soccer group will participate in soccer drills and other fitness routines (two 1-hour sessions per week). They will meet with the soccer coach after the soccer sessions to discuss the lifestyle education topics (Life's Simple 7 education topics). During the soccer sessions participants will be fitted with a wearable soccer-specific device to measure how much they move and their heart rate.

Informed Consent Process:

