Participants will receive a \$20 gift card for each assessment visit plus a parking voucher (total compensation value \$52). Subjects that complete the study will be allowed to keep the Garmin fitness tracker.

Data Analytics and Statistical Plan:

Descriptive analysis will be performed to assess the study primary aims. All statistical tests will be 2-sided, and the significance level will be set at 0.05. Data will be assessed for normality and reviewed for outliers and missing values. Mathematical transformations may be applied to meet normality assumptions. All primary analyses will be performed using the intention-to-treat principle to estimate the effects of the program.

Moreover, we will estimate the intervention efficacy using as-treated analysis, where participants are classified according to the number of sessions actually attended (i.e. the dose-response will be evaluated). To assess the effect of the proposed intervention program between baseline and 3 months, to compare the differences in the changes of the primary outcome of BMD and secondary outcomes, multilevel longitudinal models (MLM) will be used to test for differences time effects while adjusting for attrition and the correlational structure within time (repeated measures). Potential covariates may include potential effects of age, smoking, alcohol use, and therapy type. Attention will also be paid to heterogeneity between subjects (random intercept effects). Given the sample size of 40 subjects, only large effect sizes will be detectable at 80% statistical power. However, the primary focus of the analysis will be to gather initial estimates on the effect sizes (group differences and intervention efficacy) to establish adequate statistical power for a future larger study. **All analysis will be conducted by [name].**

Training of study team:

As stated above all staff and soccer coaches will receive adequate training of all study procedures. All study staff and collaborators will take CITI training upon hire.

Confidentiality: All participants will receive a study ID and this will be used on all paper and electronic forms. We will destroy all identifiers and any audio from key interviews after the study is complete.

References

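### The plan compares changes between groups without specifying baseline adjustment, which costs precision for secondary outcomes with low to moderate baseline-to-follow-up correlation

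*Combined protocol and SAP*

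**What the plan says.** The Data Analytics and Statistical Plan states its target as "to compare the differences in the changes of the primary outcome of BMD and secondary outcomes", over the interval from baseline to 3 months. The method is a multilevel longitudinal model with a random intercept per man. On covariates it says only "Potential covariates may include potential effects of age, smoking, alcohol use, and therapy type". The outcome's baseline value is not on that list. The section does not write out the fixed effects, does not say whether the groups share a common mean at baseline, and does not mention ANCOVA. Testing is conventional: "All statistical tests will be 2-sided, and the significance level will be set at 0.05".

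Study Assessments places clinic visits at baseline and after the intervention, and puts randomization after the baseline measurements: "they will be randomized to either the soccer group or the mobile health (mHealth) group".

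The documents disagree on whether there is a group comparison and on how many men are in it. Aim 1 reads "We will conduct a single-arm clinical trial over 3 months", yet the Protocol Synopsis calls the study a randomized controlled trial and Aim 2 says "we will evaluate between-group differences over 3 months in". The synopsis has "Planned Sample Size: 20 subjects"; the statistical section has "Given the sample size of 40 subjects, only large effect sizes will be detectable at 80% statistical power".

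**The concern.** A statistician following this section would most naturally fit group, time and group-by-time with a random intercept. With complete data at two visits, the interaction is then exactly the difference in mean change. A change score subtracts the whole baseline value, although only a fraction r of it (with equal SDs at both visits) predicts follow-up. When r is well below 1, this adds noise and over-corrects any chance difference between the groups at baseline.

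The plan's declared purpose is to obtain effect-size estimates for powering a larger study. Extra variance, or a shift from chance imbalance, would pass straight into that calculation. Aim 1b lists outcomes where moderate r is plausible: bone turnover markers, quality of life, self-efficacy and fitness. The open choice matters too, because the same class of model gives different estimates with and without a group term at baseline.

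**Working it through.** **Inputs.** From the documents: two-sided alpha 0.05, 80% power, N = 20 or 40, two time points, random intercept. Assumed: 1:1 allocation, equal SD at both visits, no dropout, and r varied, because no SD, correlation, allocation ratio or dropout rate is given.

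**The plan's own figure.** The plan says only that large effects are detectable with 40 men, with no number to test. With 20 per group, the detectable standardized difference is (1.960 + 0.842) × √(2/20) = 0.89, or 0.91 with the t distribution. That fits the word large. With 10 per group it is 1.25, or 1.32 with t.

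**What the model estimates.** In four simulated data sets (10 per group, r = 0.6), the random-intercept model with group, time and group-by-time matched the difference in mean change each time. Dropping the group term at baseline, which imposes a common baseline mean, moved the estimate towards ANCOVA:

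| Change score and full model | Common baseline mean | ANCOVA |
|---|---|---|
| 0.447 | 0.315 | 0.299 |
| −0.128 | −0.174 | −0.177 |
| 0.076 | −0.616 | −0.759 |
| 0.255 | 0.129 | 0.129 |

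**Variance.** With n per group and outcome SD σ:

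- difference in change: 2σ²(1 − r) × 2/n
- ANCOVA: σ²(1 − r²) × 2/n
- ratio: (1 − r²) / [2(1 − r)] = (1 + r)/2

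Estimating the slope multiplies the ANCOVA variance by 1 + 1/(N − 4). This is 1 + 1/16 = 1.0625 at N = 20 and 1 + 1/36 = 1.028 at N = 40.

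| r | (1 + r)/2 | N = 20 | N = 40 |
|---|---|---|---|
| 0.5 | 0.75 | 0.80 | 0.77 |
| 0.7 | 0.85 | 0.90 | 0.87 |
| 0.9 | 0.95 | 1.01 | 0.98 |
| 0.95 | 0.975 | 1.04 | 1.00 |

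Simulation at N = 20 (20,000 trials per value) gave 0.79, 0.90 and 1.03 at r = 0.5, 0.7 and 0.95. Break-even at N = 20 is r = 2/1.0625 − 1 = 0.88. At r = 0.99 the ratio is 1.06, close to the ceiling of 1.0625.

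In detectable differences at 80% power (t-based, N = 20, in outcome SDs), change score against ANCOVA is 1.32 against 1.19 at r = 0.5, 1.03 against 0.98 at r = 0.7, and 0.42 against 0.43 at r = 0.95.

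**Chance imbalance.** The baseline gap between groups has SD √(2/10) = 0.447 outcome SDs at 10 per arm and √(2/20) = 0.316 at 20 per arm. The probability of a gap of at least 0.45 SD in either direction is 2[1 − Φ(0.45/0.447)] = 31% and 2[1 − Φ(0.45/0.316)] = 15%. Given a gap g, the expected change-score difference moves by −(1 − r)g. For g = 0.45 the size is 0.3 × 0.45 = 0.135 SD at r = 0.7, 0.5 × 0.45 = 0.225 SD at r = 0.5, and 0.05 × 0.45 = 0.02 SD at r = 0.95.

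**The case against.** The strongest reply is that the plan never says it will leave baseline unadjusted. It writes out no fixed effects, its covariate list is open-ended, and a longitudinal model with a common baseline mean belongs to the class it names. That is correct. A reader might infer that non-adjustment is the declared method; the text supports only that it is the natural reading. What remains is that the two fits give different estimates and the plan does not choose between them.

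A second reply is scope. A reader might infer that intervals for most outcomes are too wide. No correlation is given, and the list includes hip BMD, weight, BMI, body fat, waist and lean mass, where r above 0.88 is plausible. There the gain could be nil or slightly negative. Even where adjustment helps, variance cuts of 20% and 10% narrow an interval by only about 11% and 5% (1 − √0.80 and 1 − √0.90).

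Third, a reader might infer that change scores are biased. Over randomizations they are not; the shift is conditional on the gap that happens to occur.

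Fourth, Aim 2's reference to group differences adds little support. It introduces activity compliance, attendance, attrition, injuries and satisfaction, several of which have no baseline value. The secondary outcomes that would benefit sit under Aim 1, which is worded as single-arm and pre versus post. If that wording stands, there is no group comparison and the point falls away. It survives because the synopsis, Study Assessments and the statistical section's own mention of group differences describe two arms.

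**Conclusion.** The point holds as a specification defect with a clear better method. Read in the usual way, the plan yields unadjusted change-score comparisons although the baseline value is available for most clinic and questionnaire outcomes. At 20 men, adjustment changes the variance by between about −20% (r = 0.5) and +4% (r = 0.95); at 40 men it gives about 23% and 13% lower variance at r = 0.5 and 0.7. It also largely removes a conditional shift of 0.14 to 0.23 SD when a 0.45 SD gap arises at r = 0.7 to 0.5.

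These sizes rest on assumed correlations, 1:1 allocation, equal SDs and complete data. The documents do not support extending the finding to BMD, to all secondary outcomes, or to a claim that the planned estimates are biased. It ranks below the contradictions over design and sample size, on which it depends.

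**What to change.** First reconcile single-arm with randomized, and 20 with 40. If two arms stand, write out the model's fixed effects. For each between-group comparison of an outcome measured before randomization, specify one of:

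- ANCOVA of the 3-month value on group and the baseline value; or
- the planned longitudinal model with a common baseline mean across groups, which also keeps men who miss the 3-month visit.

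Make the choice before any outcome data are seen, and report the adjusted difference with its 95% CI.

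The change does not apply to attendance, satisfaction or injuries, which have no baseline. Two outcomes need their time points settled first: dietary recall is scheduled at baseline and 26 weeks, which does not match a 3-month analysis, and no wear period before the intervention is stated for the activity tracker.

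For the clinic and questionnaire outcomes the cost is wording, one degree of freedom, and at 20 men about 4–6% more variance where the correlation is very high.

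### The only power statement assumes 40 subjects while the plan enrols 20, and it cannot be corrected until the protocol settles whether the trial is randomised or single-arm

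*Combined protocol and SAP*

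**What the plan says.** **Sample size.** The power sentence in the Data Analytics and Statistical Plan is "Given the sample size of 40 subjects, only large effect sizes will be detectable at 80% statistical power". It gives no numerical effect, SD, test or allocation ratio. The Protocol Synopsis has "Planned Sample Size: 20 subjects". Aim 1 has "Participants (n=20) will be offered an intensive intervention including RS programming and lifestyle education". Study Assessments has "Once baseline measurements are complete and 20 participants have completed they will be randomized", to either the soccer or the mHealth group.

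**Design.** The synopsis describes "A randomized controlled trial to compare two lifestyle intervention deliveries". Aim 1 says "We will conduct a single-arm clinical trial over 3 months" and plans a pre/post comparison. Aim 2 returns to two groups: "we will evaluate between-group differences over 3 months in". The Setting paragraph and Study Assessments also refer to randomised participants, and the analysis section mentions group differences.

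**Purpose.** Directly after the power sentence, the analysis section says that "the primary focus of the analysis will be to gather initial estimates on the effect sizes", to be used in powering a larger study. All tests are two-sided at 0.05.

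**The concern.** The sample size behind the power claim is twice the one the protocol plans to enrol. The sentence also cannot be repaired on its own. In a two-arm trial the relevant quantity is a difference between arms in 3-month change; in a single-arm trial it is a mean within-person change. The two have different standard errors and answer different questions, and the protocol supports both readings.

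If the 20 are randomised, a reader who relies on the sentence will believe the trial is better able to detect a difference than it is, and may read too much into a null between-group result. The effect-size estimate passed to the larger study will also be less precise than 40 subjects would give. If the study is single-arm, the sentence has the wrong sample size and does not describe the planned comparison, so the reader has no correct figure.

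**Working it through.** **Inputs from the document.** Two-sided alpha 0.05; power 80%; sample size 40 (power sentence) or 20 (synopsis, Aim 1, Study Assessments).

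**Assumptions, because the document is silent.** 1:1 allocation; no dropout (10% and 20% shown as a range); effects in SDs of the 3-month change, since no SD for lumbar spine BMD change is given; a large effect taken as about 0.8 SD or more.

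**Test.** A t-test on the change scores. With two time points, complete data and no covariates this matches the planned random-intercept model. In three simulated data sets the group-by-time statistic agreed with the two-sample t on change, and the time statistic agreed with the paired t. Covariate adjustment or missing data would alter the figures.

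**Formulas.** Normal approximation, with 1.960 + 0.842 = 2.802:
- two arms, n per arm: d = 2.802 × √(2/n)
- single arm of n: d = 2.802 / √n

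The reported figures use the noncentral t, which is slightly larger at these sample sizes. The 95% CI half-width is t × √(1/n₁ + 1/n₂) for two arms and t/√n for one arm, in SD units.

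**What the sentence can mean at 40.** There is no stated number to reproduce, so only the word large can be checked.
- 20 per arm: 2.802 × √(2/20) = 0.89; noncentral t 0.91 SD. This fits a claim that only large effects are detectable.
- Single arm of 40: 2.802/√40 = 0.44; noncentral t 0.45 SD. This does not fit.

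The sentence therefore reads most naturally as a two-arm trial with 20 per arm. That is an inference, not something the document states.

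**What 20 subjects give.**
- 10 per arm: 2.802 × √(2/10) = 1.25; noncentral t 1.32 SD.
- Single arm of 20: 2.802/√20 = 0.63; noncentral t 0.66 SD.

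| Design | Effect with 80% power (SD of change) | Power at 0.8 SD | 95% CI half-width (SD) |
|---|---|---|---|
| 20 vs 20 | 0.91 | 69% | 2.024 × √(1/20 + 1/20) = 0.64 |
| 10 vs 10 | 1.32 | 39.5% | 2.101 × √(1/10 + 1/10) = 0.94 |
| Single arm, 20 | 0.66 | 92% | 2.093/√20 = 0.47 |

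Power at 0.91 SD, which is 80% with 20 per arm, is 49% with 10 per arm.

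**Range under other assumptions.** Two arms: 12 vs 8 needs 1.35 SD; 9 vs 9 (10% loss) needs 1.41 SD; 8 vs 8 (20% loss) needs 1.51 SD. Single arm: 18 completers need 0.70 SD; 16 completers need 0.75 SD.

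The two-arm and single-arm figures should not be ranked against each other. One is a contrast between arms; the other is an uncontrolled change.

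**The case against.** The sentence claims only that large effects are detectable. At 10 per arm the threshold of 1.32 SD is still large, so the wording remains literally true, and it already warns against over-reading a null result. The fall from 80% to 49% starts from 0.91 SD, which is inferred from the sentence under an assumed two-arm 1:1 design and an outside convention for what counts as large. In the single-arm case the wording is, if anything, cautious. This is an internally funded pilot, its sample size was not derived from the power claim, and it puts estimation first. The randomised versus single-arm conflict is also a larger problem than one sentence about power.

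Much of this stands. It limits the consequence to moderate, and the 0.91 SD baseline must be labelled as an inference. It does not remove the error. No assumption is needed to see that 40 and 20 disagree, and no reading of the text reconciles them: nothing says that 20 is per arm or a first batch, and the synopsis gives it as the planned total. Literal truth at 10 per arm is little comfort when the effect needed is about 1.32/0.91 = 1.45 times as large. An emphasis on estimation also makes precision matter more, and the half-width grows from 0.64 to 0.94 SD. These half-widths treat the SD as known; allowing for its estimation changes the 10-per-arm and single-arm figures only to about 0.93 and 0.46. The design conflict does reach further, but it has to be settled before this sentence can be corrected.

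**Conclusion.** The concern holds. The protocol's only power statement rests on a sample size that appears nowhere else and is double the planned enrolment, and the correct replacement depends on a design question that the protocol leaves contradictory.

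If the 20 are randomised, the sentence overstates what the trial can detect, relative to the 20-per-arm reading. If the study is single-arm, there is no loss of power for a large change, but the sentence has the wrong sample size and does not describe the pre/post analysis. The mismatch itself is certain; the sizes rest on the assumptions listed with the calculation. It should be fixed, but it does not undermine a pilot whose main product is an estimate and in which no decision depends on the power claim.

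**What to change.** First settle one design and one sample size, and make the Protocol Synopsis, Aims 1 and 2, Setting, Study Assessments and the Data Analytics and Statistical Plan agree. Then replace the power sentence with the version that applies.

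- **Two arms:** With 20 participants (10 per arm, no dropout), 80% power at two-sided 0.05 requires a between-arm difference in 3-month change of about 1.32 SD of the change; a difference of 0.8 SD has about 40% power; the expected 95% CI half-width is about 0.94 SD.
- **Single arm:** With 20 participants (no dropout), 80% power at two-sided 0.05 requires a mean 3-month change of about 0.66 SD of the change; the expected 95% CI half-width is about 0.47 SD.

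Because the plan expects some attrition, add the corresponding range for 10% to 20% loss: 1.41 to 1.51 SD for two arms, or 0.70 to 0.75 SD for a single arm. If allocation is not 1:1, recompute.

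If 40 is the intended sample size, the synopsis, Aim 1 and Study Assessments must say so instead.

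**Cost.** Wording only, once the design is settled, and no extra participants if the sample size stays at 20. For two arms the stated figure becomes less favourable. If 40 is intended, the cost is 40 − 20 = 20 more participants than the synopsis plans.
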